4.2 Obtaining Identifiable Information About Non-Subjects

N/A

4.3 Number of Subjects

A. Total Number of Subjects

Overall, we will have a total number of 1605 participants. This includes the cognitive testing (n=30), the cRCT (n=510 tryads; 1530 participants total) and the process evaluation (n=45).

Cognitive testing: We will recruit a total of 30 participants for the cognitive testing.

cRCT: We will recruit 5 mother, father and child triads in each of the 104 villages included in our sample. Our total sample will include 510 dyads. We will also ask the head of the farming group to complete a survey about the village.

Process evaluation: We will include a maximum of 45 participants in the semi-structured interviews/focus groups conducted as part of the process evaluation.

B. Total Number of Subjects If Multicenter Study

N/A

C. Feasibility

Based on our previous experience, we were able to recruit participants from the study villages efficiently. Our response rate in our previous large cross-sectional survey of ~1200 households was ~95%. Our enumeration teams (which will be composed of in the same way in our present study) were able to recruit and conduct extensive household surveys (~2 hrs in duration) with ten households per team, per day. We have planned for our enumeration teams to recruit and conduct household surveys with the same number of households in this study. However, the household surveys will be significantly shorter than our previous work (~45 minutes in duration).

Our mHealth messaging intervention will be 16 weeks in duration. Given the relatively short length of intervention time, as well as the low participant burden associated with participation, we do not anticipate having significant difficulties with participant retention. Our pilot study found an attrition rate of 2%. Our sample size calculation is based on an attrition rate of 5% and we have sufficient power to detect changes in our effect sizes (6% absolute difference in anemia; 7% absolute difference in MAD) even with 10% attrition.

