cRCT sample. The villages in which we are conducting this study are subsistence farming communities with high levels of poverty and malnutrition in three regions of Senegal: Thies, Diourbel and Fatick. Each of the 104 villages that will be included in the study have been purposively selected to ensure that they have an established farming group, and that they are sufficiently geographically dispersed in order to minimize risk of contamination. We will use the list of the household members of the farming groups of each of the 104 villages included in the cRCT as our sampling frame. Based on [name] previous experience, we will identify all households within the farming group that have a child 6-19 months of age at baseline (to ensure that the child is not >23 months at endline), and we will subsequently randomly select five mother, father and child triads to be included in our study sample. In some cases, the primary caregiver of the child may be a close relative rather than the birth mother. In these instances, the primary caregiver will receive the voice and text messages along with her husband or primary male caregiver. In total, we will sample 510 triads in 104 villages (~5 households/triads per village). Thus, our sample will include 510 mother, father and child triads. Baseline data collection will take place in May/Jun 2022, the intervention will be delivered between Jun-Sep 2022 and the endline data collection will take place in October 2022.

Process Evaluation sample: A smaller purposive sample of approximately 45 mothers and fathers, implementation project staff and CHWs will be included in Aim 2 of the project as part of the in-depth semi-structured interviews and focus groups conducted in the process evaluation. We will purposively select three villages from each region (n total = 9 villages) in order to maximize variation in village characteristics such as size, distance to urban settings, distance to markets, etc. Interviewees and focus group participants will be purposively selected from the list of all mothers and fathers receiving the voice messages in each of these villages to ensure variation in participant socio-demographics (e.g., household size, parity, age, etc.) as well as key people involved in the intervention's implementation. The process evaluation data collection will take place in between October and December 2022.

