1.5 Sample Size Justification

We expect to enroll 510 mother, father and child triads in 104 villages (clusters) in the Thies, Diourbel and Fatick regions of Senegal as part of this study. We plan to include ~5 triads per village. Our sample size estimation was calculated based on our two primary outcomes: the prevalence of MAD and anemia.

The sample size estimate is informed by our prior cross-sectional research on over 1200 household surveys and our pilot data over a 4-week intervention period (unpublished data).² Attrition was 2%, anemia prevalence was 66% and MAD prevalence was 46.8%. Assuming a conservative intra-class correlation coefficient of 0.02,³ 5% attrition (based on our pilot work and previously published community-based research projects in Senegal),^{29,30} and a 2-sided significance level of 0.05, 102 clusters with 5 triads per cluster will provide 81.7% power to detect a 6% absolute difference in anemia and 88.8% power to detect an absolute difference of

7% in MAD. Our pilot study found a 19.2% increase in MAD. Even if we assume 10% attrition, we will still have 80% power to detect a 6% absolute difference in anemia and 87.3% power to detect an absolute difference of 7% in MAD. Improvements in anemia and MAD prevalence of 6% and 7%, respectively are clinically relevant and aligned with improvements in previously published studies.^{31,32}

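### Five triads in each of 104 villages makes 520, but the protocol states 510, which is the 102 × 5 of its power calculation; the totals of 1,530 and 1,605 inherit the mismatch

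*Protocol*

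**What the plan says.** **Per-village target.** Section 4.3 is unqualified: "We will recruit 5 mother, father and child triads in each of the 104 villages included in our sample". Section 4.1 agrees: five households are drawn at random from each farming group, and oversampling is planned so that five are obtained in every village. The sample description in section 1.3 first selects five triads per village, then softens this in its total: "In total, we will sample 510 triads in 104 villages (~5 households/triads per village". Section 1.5 also uses an approximate five.

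**Total.** Section 4.3 follows its per-village sentence with "Our total sample will include 510 dyads". Its count of people reads "the cRCT (n=510 tryads; 1530 participants total", and the grand total is "Overall, we will have a total number of 1605 participants". Sections 1.3 and 4.1 also pair 510 triads with 104 villages.

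**Clusters.** Section 1.5 opens with "We expect to enroll 510 mother, father and child triads in 104 villages (clusters" and then attaches the stated power to "102 clusters with 5 triads per cluster". The randomisation paragraph in section 1.3 allocates 104 villages 1:1. Nothing explains the two additional villages.

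**Process evaluation.** About 45 people take part. Sections 1.3 and 4.1 draw the mothers and fathers among them from those already receiving the messages; project staff and community health workers make up the rest. The split is not given.

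The SAP contains no sample size, so it does not settle the matter.

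**The concern.** Two consecutive sentences of the section that defines the number of subjects cannot both be met: five in each of 104 villages does not give 510. Villages, triads and participants are the figures that the ethics submission, the recruitment plan and the eventual participant flow diagram all draw on. A team that follows the per-village sentence enrols 30 more people than the section's own total. A team that stops at 510 leaves up to ten villages short of five, and no rule says which. The power statement rests on a third configuration, 102 clusters, which is not the number randomised.

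**Working it through.** **Inputs.** 104 villages (sections 1.3, 1.5, 4.1, 4.3); 5 triads per village, unqualified (4.1, 4.3) or approximate (1.3, 1.5); 510 triads (1.3, 1.5, 4.1, 4.3); 102 clusters of 5 (1.5); 30 cognitive-testing and 45 process-evaluation participants (4.3).

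**Step 1: reproduce the stated figures.**
- Triads = clusters × triads per cluster = 102 × 5 = 510.
- Trial participants = 3 × 510 = 1,530.
- Overall = 30 + 1,530 + 45 = 1,605.

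All three stated totals follow, but only from 102 villages.

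**Step 2: apply the per-village rule to the villages randomised.**
- 104 × 5 = 520 triads.
- 3 × 520 = 1,560 trial participants.
- 30 + 1,560 + 45 = 1,635 overall.
- Gap: 520 − 510 = 10 triads, or 30 people; 10/510 = 2.0%.

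**Step 3: test the approximate wording.** 510/104 = 4.90 per village. This fits an approximate five, so the totals in sections 1.3 and 1.5 can stand on that reading. It does not fit a fixed five in every village.

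**Step 4: the overlap in the overall total.** Parents in the process evaluation are already in the 1,530. Between 0 and 45 of the 45 could be parents, so the number of distinct people lies between 30 + 1,530 = 1,560 and 1,605 with 510 triads, or between 30 + 1,560 = 1,590 and 1,635 with 520. The true figure is inside these limits, because the 45 include both parents and staff.

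**Step 5: effect on power of 104 rather than 102 clusters of 5.** Only the change matters here, so I computed it in two ways.
- *Taking the stated power at face value.* With all else equal, the standardised effect grows by √(104/102) = 1.0098. For anemia, 81.7% power corresponds to 1.960 + 0.904 = 2.864; multiplied by 1.0098 this is 2.892, giving 82.4% (+0.7 points). For MAD, 88.8% corresponds to 1.960 + 1.216 = 3.176; multiplied by 1.0098 this is 3.207, giving 89.4% (+0.6 points).
- *From the stated inputs, assuming a simple endline comparison of proportions.* Effective n per arm = (clusters/2) × 5 × 0.95 / [1 + (5 − 1) × 0.02], which is 51 × 4.75/1.08 = 224.3 for 102 clusters and 52 × 4.75/1.08 = 228.7 for 104. (The even halves of 51 and 52 are a calculating convenience.) The gain is 0.4 points for anemia (66% vs 60%) and 0.5 points for MAD (46.8% vs 53.8%). With a difference-in-differences variance factor of 2(1 − ρ), and ρ, the unstated baseline–endline correlation, assumed anywhere from 0 to 0.9, the gain stays below 0.9 points.

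Both routes give about half a point, in the trial's favour.

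**The case against.** The strongest defence is that the totals in sections 1.3 and 1.5 are openly approximate, and that 4.90 per village is what an approximate five means. That stands for those sentences. It does not reach sections 4.1 and 4.3, where five is fixed and backed by oversampling.

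A reader might infer that 102 versus 104 clusters is a contradiction in itself. The documents do not support that. A calculation on 102 clusters followed by randomisation of 104 is a margin in the safe direction. What is missing is a sentence explaining it. That 510 was carried over from the 102-cluster calculation is likely, but it is an inference.

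A reader might also infer that field teams have no workable instruction. They do: select five per farming group and oversample to secure five. Following it meets or exceeds the 102 × 5 basis, and the only figures exceeded are the stated totals.

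Finally, baseline was planned for May/June 2022 and the SAP is dated 05/21/24. If that schedule held, guidance to field teams comes too late. The denominators for reporting still need to be right.

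**Conclusion.** The point holds as a reconciliation item. Section 4.3 contradicts itself by 10 triads (30 people, 2%), and 1,530 and 1,605 are correct only if 510 is. The overall total also double-counts some process-evaluation parents. That overlap is real, but the documents give no split of the 45 from which to compute it.

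It would be wrong to read this as a threat to validity or as evidence of inadequate power. The randomisation scheme, the effect being estimated and the analysis model are untouched, and enrolling 520 adds about half a point of power (below one point on every assumption tried). Whether the stated power levels themselves follow from the stated inputs is a separate question: nothing here depends on it, and correcting 510 or 520 would not answer it.

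The contradiction rests on reading five per village in sections 4.1 and 4.3 literally. The oversampling sentence supports that reading.

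**What to change.** Choose one configuration and use it in sections 1.3, 1.5, 4.1 and 4.3:

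- **Option A:** 104 villages × 5 = 520 triads and 1,560 trial participants; 1,635 overall before the process-evaluation overlap is removed.
- **Option B:** keep 510 triads and 1,530 participants, state an average of about 4.9 per village, and reword the fixed five in 1.3, 4.1 and 4.3, including the oversampling sentence.

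Under either option:
- base the sample size statement on the 104 clusters randomised, or say why 102 was used;
- write triads throughout, replacing dyads;
- state that process-evaluation parents are a subset of trial participants, give the planned split of the 45, and count only the others as additional.

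Do not write a fixed number of villages per arm unless the stratified allocation guarantees it; the protocol gives only a 1:1 ratio.

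The cost is wording changes in four sections. Option A raises the stated participant total and may need a notification to the ethics committees. If enrolment is complete, report the villages, triads and people actually enrolled and explain any difference from 510.

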4.4 Consent Procedures

A. Consent Process

- **Location of Consent Process**

The enumerators will meet with participants in their household yards/compounds or another location in the community, as preferred by the participant. At the end of the recruitment and consent process, we will coordinate with the participant to schedule the timing and location of the survey.

- **Ongoing Consent**

This research is of short duration. The intervention is only 16 weeks. For this reason, we will not obtain ongoing consent throughout the research project.

- **Individual Roles for Researchers Involved in Consent**

As mentioned, the consent process will be conducted by our team of local enumerators. They have extensive experience conducting research in these study communities.

The local enumerator will obtain consent in their local language (i.e., Wolof, Serere, or Pular). The enumerators have a substantial amount of experience doing these types of surveys and

interviews. [name] has been working closely with these enumerators since 2015. All of the enumerators have at minimum a Bachelor's degree and are proficient in French, Wolof and, in many cases, Serere and Pular.

- **Consent Discussion Duration**

We anticipate the consent discussion taking approximate 10-15 minutes to complete, based on our previous experience working in these communities.

- **Coercion or Undue Influence**

We will stress that participation in the study is voluntary and that potential subjects are under no circumstances obligated to participate.

- **Subject Understanding**

Subjects will be provided with a copy of the consent form that describes the study. They will also have contact information for members of the study team in the case where they wish to have additional information. Lastly, they will have the opportunity to ask questions during the recruitment process.

- **Protecting Privacy**

We will make every effort to obtain consent in privacy (without any peers or family members present, as described above).

B. Waiver or Alteration of Consent Process

- **Waiver or Alteration Details**

We are not requesting a waiver of consent.

- **Destruction of Identifiers**

We are not requesting a waiver of consent.

- **Use of Deception/Concealment**

This research does not involve deception or concealment.

- a. **Minimal Risk Justification**

N/A

- b. **Alternatives**

N/A

- c. **Subject Debriefing**

N/A

C. Documentation of Consent

- **Documenting Consent**

Written consent in the form of a signature will be obtained on the consent form. We have previously worked in these communities and have found people to be able to sign consent forms. Although the literacy levels in these communities are low, the majority of people are able to print their names. Those that are not able to print their names draw an X on the consent form.

- **Waiver of Documentation of Consent (i.e., will not obtain subject's signature)**

N/A

4.5 Special Consent Populations

A. Enrolling Minors-Subjects Who Are Not Yet Adults

- **Parental Permission**

We will obtain consent from parents/guardians of young children to participate in this research.

- **Non-Parental Permission**

We will obtain consent from parents of young children. However, in some cases the child may be under the care of a legal guardian rather than parent. In these cases, we will obtain consent from the legal guardians.

- **Assent Process**

We are including young children in this study; however, they are too young to provide assent. The infants included in this study will be between 6-23 months of age (i.e., less than 2 years old). At this age, children are incredibly limited in their ability to speak and from a developmental perspective cannot reasonably be consulted to provide assent. For this reason, we are not seeking assent from infants and young children.

- **Documentation of Assent**

N/A

- **Reaching Age of Majority During Study**

N/A

B. Enrolling Wards of the State

N/A

- **Research Outside of NJ Involving Minors**

Our data will be collected in Senegal according to local IRB requirements. There are no specific laws pertaining to research involving minors that we need to adhere to.

C. Enrolling Non-English-Speaking Subjects

The participants in this study speak French, Wolof and/or Pular.

- **Process for Non-English-Speaking Subjects**

All information regarding the study will be communicated orally to participants in their local language (i.e., Wolof or Pular). Given the low literacy rates in these communities it is imperative that the consent form be explained orally. Moreover, Wolof – the language spoken by the majority of participants – is not a written language. Therefore, consent forms will be written in

French but explained in the local language. This is the approach recommended by the Senegal National Ethics Committee.

- **Short Form Consent for Non-English Speakers**

We will not be using the short form consent.

D. Enrolling Adults Lacking Decision-Making Capacity (Surrogate Consent)

We will not enroll participants who lack decision-making capacity.

- **Assessing Adult Capacity to Consent**

N/A

- **Selecting a Surrogate & Consent Process**

N/A

- **Subject Assent**

N/A

- **Selecting a Witness to the Surrogate Consent Process**

N/A

- **Removing a Subject**

N/A

E. Special Consent Considerations

As mentioned previously, the consent forms will be read out loud to potential participants given the low literacy rates in the study communities.

4.6 Economic Burden and/or Compensation for Subjects

A. Expenses

Study participants will not incur any costs related to participating in this project.

B. Compensation/Incentives

Subjects participating in cognitive testing will receive \$5 USD for their participation.

C Compensation Documentation

We will make a list of all interviewees using unique identification numbers rather than their names (in order to not collect identifying information) and mark with a check next to their ID number once they have completed the interview and received their compensation.

4.7 Risks of Harm/Potential for Benefits to Subjects

A. Description of Risks of Harm to Subjects

- **Reasonably Foreseeable Risks of Harm**

This study poses only minimal risks to participants. The potential risks to study participants include temporary discomfort related to the assessment of hemoglobin levels using a finger prick. However, the hemoglobin assessment is a minimal risk procedure.

There are no known side effects of participating in the intervention. The intervention consists of providing IYCF information to mothers and fathers of young children (6-23 months). However, it is possible that mothers and fathers could misunderstand the nutrition messages resulting in poor diet and nutrition practices. We will conduct cognitive testing prior to the delivery of the intervention in an effort to eliminate this risk.

There is also the inconvenience of the time required for listening to/reading the messages, responding to the surveys, and participating in the semi-structured interviews and focus groups. The risks are limited to the immediate study period. With regards to severity, we do not anticipate any severe risks from participating in the study.

- **Risk of Harm from an Intervention on a Subject with an Existing Condition**

We do not anticipate any risk of harm from the intervention for subject's with existing conditions.

- **Other Foreseeable Risks of Harm**

There is the potential risk of loss of confidentiality. Risk of breach of confidentiality will be minimized in several ways. First, all participants will be assigned a coded identification number to assure that their identifying information is not linked to their data. A single list linking participant identification numbers with participant names will be kept in a locked electronic file on the computer of the PI. Research staff will operate under explicit guidelines to preserve confidentiality when speaking to participants. All materials with identifying information will be kept in locked files. Furthermore, confidentiality is enhanced by the use of computer-administered surveys, and data collection will be such that only an encrypted password will allow study researchers to access study data. No participant names or identifying information will be stored in the database – all data will be de-identified. All research staff will be trained in ethical guidelines governing research, including obtaining certification in the Collaborative Institutional Training Initiative.

While every possible step is taken to minimize risks, if participants have any concerns about any aspect of the study, consent documentation makes it clear that they can refuse to continue with the study at any time without penalty. The consent forms will also contain the contact information for the CNERS local IRB, [name], the Project Coordinator, and [name] in case they wish to speak to the IRB or a member of the study team to discuss adequacy of protection against risks.

- **Observation and Sensitive Information**

N/A.

B. Procedures which Risk Harm to Embryo, Fetus, and/or Pregnant Subjects

None.

C. Risks of Harm to Non-Subjects

There will be no risks of harm to non-subjects in this study.

D. Assessment of Social Behavior Considerations

There are few possible risks of participating in this study. Some possible risks include misunderstanding of nutrition messages resulting in poor diet and nutrition practices. Participants may feel uncomfortable sharing their attitudes and beliefs but they are not obligated to share anything that they do not want to share. There may also be tension between participants trying to change their IYCF practices and people they know who advocate for other practices. This may cause strain in social interactions and relationships. There is also the inconvenience of the time required for listening to the messages, responding to the surveys, and participating in the semi-structured interviews (for participants in the process evaluation).

E. Minimizing Risks of Harm

We will minimize risk by making the nutrition education messages as clear as possible and making sure they are conveyed in a language that is easy to understand. We have also shared the voice messages with the *Senegalese Committee for Nutrition Development* to ensure that they are in line with their efforts to improve nutrition education in Senegal.

We will also engage participants in an open dialogue that takes into account their culture, education, and other factors to be inclusive of everyone. We will ensure that all participants fully understand the study, risks and benefits, as well as their right to cease participation in part or all of the study at any time.

- **Certificate of Confidentiality**

Given that this is a NIH funded study, this study has been automatically issued a certificate of confidentiality. We have included language that refers to this in our consent forms.

- **Provisions to Protect the Privacy Interests of Subjects**

All surveys will be done individually to protect the participants' privacy. We do not anticipate that the questions asked will be considered sensitive.

F. Potential Direct Benefits to Subjects

Potential benefits to participants include increasing their knowledge related to IYCF practices, which could lead to improvements in dietary quality (e.g., minimum acceptable diet) and nutrition outcomes (e.g., anemia) as well as improved growth and development in their young children.

